9.3. Biomarker Measurements

A blood sample will be collected for assessment of galectin-3 at Infusion Visits 1, 7, 13, 20, and 14 to 28 days after final infusion. Summary statistics of the observed values and change from baseline will be provided at the scheduled visits for the safety population.

9.4. Vital Sign Measurements

Vital sign measurements including respiratory rate (bpm), heart rate (beats per minute), temperature (C), systolic blood pressure (mmHg), diastolic blood pressure (mmHg), weight (kg) and BMI (kg/m^2) will be summarized descriptively using the safety population

at the scheduled visits. Change from baseline values will also be summarized descriptively at the scheduled visits. All vital signs will be presented in a listing.

9.5. Physical Examination

A complete physical examination will be performed at screening, with particular attention to examination for stigmata of liver disease/cirrhosis. A limited physical examination will only include weight and examination of the heart, lung, and abdomen during the treatment phase.

The number and percentage of subjects with each physical examination outcome (normal, abnormal, or not done) will be summarized using the safety population by body system at scheduled visits. Also the number and percentage of subjects with change from baseline will be presented in a shift table by body system at the post-baseline scheduled visits.

All physical examination results will be presented in a listing.

9.6. Electrocardiogram (ECG)

12-lead ECG assessments including PR interval (milliseconds), QRS interval (milliseconds), QT interval (milliseconds), and QTc interval (milliseconds) will be summarized descriptively using the safety population at the scheduled visits. Change from baseline values will also be summarized descriptively at the scheduled visits,

The number and percentage for ECG overall interpretation (normal or abnormal and not clinically significant vs. clinically significant,) will be summarized at scheduled visits. Also the number and percentage of subjects with change from baseline will be presented in a shift table at the post-baseline scheduled visits.

All ECG assessments will be presented in a listing.

10. Pharmacokinetics

All PK analysis will be conducted using the PK population.

10.1. Plasma Concentrations

PK blood samples will be collected at the following times:

- Infusion Visit 1: Approximately 2 hours following the end of the infusion, on the day following the infusion (Nondosing Visit 1 [ie, Day 2]), and on Nondosing Visit 2 (ie, Day 3) following the infusion. The blood sample collections on Nondosing Visits 1 and 2 (ie, Days 2 and 3) can occur at any time during those days.
- Infusion Visit 2: Approximately 2 hours following the end of the infusion
- Infusion Visit 3: Approximately 2 hours following the end of the infusion
- Infusion Visit 4: Approximately 2 hours following the end of the infusion and on Nondosing Visit 3 (which can be either Day 2 or 3 following the infusion). The

blood sample collection on Nondosing Visit 3 (ie, Day 2 or 3) can occur at any time during those days.

- Infusion Visit 7: Any time after the end of infusion on the day of the infusion.

The individual plasma concentrations of GR-MD-02 will be listed for each subject. The listing will include subject number, dose group, scheduled visit, date and time of collection, actual relative time to dose, and plasma concentrations. All concentrations below the limit of quantification (BLQ) or missing data will be labelled as such in concentration data listings.

GR-MD-02 concentrations will be summarized using descriptive statistics by dose group, visit, and scheduled time point. Descriptive statistics will include arithmetic mean, SD, coefficient of variation (CV), minimum, median, maximum, geometric mean and geometric mean CV. Concentrations that are BLQ will be treated as zero in the summary statistics of concentration data. All missing concentrations will be treated as missing in the summary statistics of concentration data.

Plots of arithmetic mean (\pm SD) concentration versus visit and time (both linear and semi-logarithmic) by dose group and individual concentrations versus visit and time (both linear and semi-logarithmic) will be provided. For ease of presentation, nominal sampling times will be used to present results in figures.

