## 2.5 Pharmacokinetic Objective

The pharmacokinetic (PK) objectives are to evaluate systemic exposure following multiple doses of GR-MD-02 in subjects with portal hypertension due to NASH cirrhosis and to explore the population pharmacokinetics of GR-MD-02 in subjects with NASH with portal hypertension and cirrhosis or advanced bridging fibrosis.

Note: Formal population PK analysis will not be performed in this study. However, GR-MD-02 plasma levels will be used to evaluate systemic exposure following multiple doses. In the Phase 1 clinical study ([Galectin 2014](#)), the observed maximum plasma or serum concentration after administration ( $C_{max}$ ) drug levels for all doses were well correlated with the area under the concentration-time curve ( $h \cdot \mu\text{g/mL}$ ) ( $p < 0.001$ ,  $r^2 = 0.91$ ). Therefore,  $C_{max}$  plasma levels at 2 hours following the dose of GR-MD-02 will be used to estimate the systemic exposure of the drug. Plasma levels of GR-MD-02 will be evaluated at the initiation of the study in all subjects, 2 hours after investigational medicinal product (IMP) infusion at Infusion Visits 1, 2, 3, 4, 7, 10, 13, and 26. Trough levels of drug will not be informative, since there were only measurable levels of drug detected through 72 hours following a dose and were thereafter undetectable (assay limit of detection of 1.2  $\mu\text{g/mL}$ ).

[figure not shown]

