## 6.5 Pharmacokinetic Assessments

Plasma levels of GR-MD-02 will be assessed in all subjects (Table 12-2). Plasma levels of GR-MD-02 will be assessed 2 hours following the infusion of IMP in all subjects after Infusion Visits 1, 2, 3, 4, 7, 10, 13, and 26. At the first data safety monitoring board (DSMB) meeting, the panel will evaluate GR-MD-02  $C_{max}$  plasma levels after Infusion Visits 1, 2, 3, and 4 for the first 30 subjects.

Blood samples for bioanalytical assay will be handled as described in the Study Manual. The date of PK blood collection must be recorded in the subject's eCRF. Each label will state the study number, subject number, matrix (plasma), and study day of the sample.

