## 10 Study Management

### 10.1 Monitoring

#### 10.1.1 Independent Data Safety Monitoring Board

A DSMB will be established that includes a panel of at least 3 independent members to include medical experts and an unblinded biostatistician. An official charter will be established and approved by all members and Galectin Therapeutics Inc. The primary role of the DSMB will be to periodically monitor the safety of the clinical study. The DSMB will meet at several predetermined times during the study and at any other time when it is determined by the DSMB or Galectin Therapeutics Inc that such a review is warranted. An organizational meeting will be held prior to the first subject randomly assigned to IMP to review and approve the DSMB Charter and to review the output to be provided to the DSMB for scheduled reviews. In addition, an unblinded monitoring team will be established.

The first scheduled DSMB review meeting will be after the first 30 subjects in the study have received 7 doses of IMP. The purpose of this early look at safety is to ensure that there are no unexpected AEs in the population being evaluated in this study. The second scheduled DSMB review meeting will occur after approximately 50% of the total number of subjects to be enrolled has received 13 doses of IMP. The DSMB will then meet again after 50% of subjects have received 26 doses of IMP.

At the first DSMB meeting, the panel will also evaluate GR-MD-02  $C_{\max}$  plasma levels after Infusion Visits 1, 2, 3, and 4 for the first 30 subjects. There should be approximately 10 subjects who received 2 mg/kg and 10 subjects who received 8 mg/kg in this group of subjects. With the aid of a clinical pharmacologist on the panel, the DSMB will assess  $C_{\max}$  levels as a surrogate for systemic exposure, with increasing number of doses in the groups receiving IMP and compare the levels to the safety margins indicated by long-term animal toxicology studies.

The investigative study center staff, subjects, the sponsor and its representatives, and representatives of the CRO, except those responsible for providing unblinded data to the DSMB, will remain blinded throughout the full duration of the study until after the database is locked at the conclusion of the blinded treatment period.

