10.2. Plasma Pharmacokinetic Parameters

GR-MD-02 plasma concentrations will be used to evaluate systemic exposure following multiple dosing. Based on the high correlation between the area under the concentration-time curve and C_{max} of GR-MD-02 in the Phase 1 clinical study (Galectin 2014) ($p < 0.001$, $r^2 = 0.91$), the plasma levels at 2 hours (approximate C_{max}) following the dose of GR-MD-02 will be used to estimate the systemic exposure and to assess the attainment of the steady state of GR-MD-02.

All PK analyses will be conducted by the Department of Clinical Pharmacology, PPD, Inc., Richmond, VA, USA.

11. Interim Analysis

An interim analysis of PK data is planned for the first Data Safety Monitoring Board (DSMB) meeting. It is expected that PK analysis will be performed on the GR-MD-02 plasma concentrations for the first 30 subjects after Infusion Visits 1, 2, 3, 4 and 7. There should be approximately 10 subjects who received 2 mg/kg and 10 subjects who received 8 mg/kg in this group of subjects.

12. Data Safety Monitoring Board

An independent Data Safety Monitoring Board (DSMB) will be composed of medical experts and an unblinded biostatistician who will not participate in the study. The DSMB will be responsible for periodically monitoring the safety of the clinical study and

providing recommendations for the study by reviewing the safety data at several predetermined times during the study and at any other time when it is determined by the DSMB or Galectin Therapeutics Inc that such a review is warranted.

The DSMB review will occur as follows:

- after the first 30 subjects in the study have received 7 doses of IMP;
- after the approximately 50% of subjects to be enrolled has received 13 doses of IMP;
- after 50% of subjects have received 26 doses of IMP.

In addition to review of the safety data, the first DSMB meeting will also assess GR-MD-02 C_{\max} plasma levels after Infusion Visits 1, 2, 3, 4 and 7 for the first 30 subjects.

13. References

Galectin Pharmaceuticals, Inc. A Multi-Center, Partially Blinded, Maximum Tolerated Multiple Dose Escalation, Phase 1 Clinical Trial to Evaluate the Safety of GR-MD-02 in Subjects with Non-Alcoholic Steatohepatitis (NASH) with Advanced Hepatic Fibrosis. 17 Jun 2014. Protocol No. GT-020. Version 4. 96p.

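### The SAP leaves the Infusion Visit 7 PK sample untimed but has the DSMB read it as Cmax beside 2-hour samples, so the latest value in that review is not comparable with the others

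*SAP*

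**What the plan says.** SAP 10.1 sets the sampling times. Visits 1 to 4 each have a sample about 2 hours after the infusion ends; the Visit 2 entry, for example, reads "Infusion Visit 2: Approximately 2 hours following the end of the infusion". Visit 1 adds samples on Days 2 and 3, and Visit 4 adds one on Day 2 or 3. The last entry is "Infusion Visit 7: Any time after the end of infusion on the day of the infusion". No later visit is listed.

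SAP 10.2 defines the measure. It treats the 2-hour level as an approximate Cmax and states that concentrations at this time "following the dose of GR-MD-02 will be used to estimate the systemic exposure and to assess the attainment of the steady state". SAP 11 plans an interim PK analysis of the first 30 subjects at Visits 1, 2, 3, 4 and 7. SAP 12 has the first DSMB meeting assess Cmax "plasma levels after Infusion Visits 1, 2, 3, 4 and 7 for the first 30 subjects".

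The supplied protocol differs. Section 6.5 takes plasma levels "2 hours following the infusion of IMP in all subjects after Infusion Visits 1, 2, 3, 4, 7, 10, 13, and 26", and Table 12-2 repeats the 2-hour time for every PK sample. Protocol 10.1.1 limits the DSMB review to Cmax "plasma levels after Infusion Visits 1, 2, 3, and 4 for the first 30 subjects".

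**The concern.** A sample with no fixed time is not a Cmax by the SAP's own definition. Visit 7 is also the latest dose in the DSMB review, so any difference in sampling time falls entirely on the comparison of late with early doses.

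That comparison is the purpose of the review. Protocol 10.1.1 asks the DSMB to look at Cmax as doses accumulate and to set it against the safety margins from animal toxicology, with about 10 subjects per active dose. A Visit 7 sample drawn soon after the infusion could look like a rise in exposure, and one drawn late could hide a rise.

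The SAP's summaries do not correct for this. Concentrations are tabulated by scheduled time point and plotted at nominal times, and Visit 7 has no clock time for either. Actual time relative to dose appears only in the listing. It is also unclear whether an untimed Visit 7 sample could by itself qualify a subject for the PK set, which requires at least one Cmax sample.

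**Working it through.** **Step 1: the schedules side by side.** Infusion Visit v falls in Week 2v − 1.

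| Infusion Visit (week) | Protocol 6.5 | SAP 10.1 | In DSMB Cmax review, protocol 10.1.1 | In DSMB Cmax review, SAP 12 |
|---|---|---|---|---|
| 1, 2, 3, 4 (1, 3, 5, 7) | 2 h | about 2 h | yes | yes |
| 7 (13) | 2 h | any time that day | no | yes |
| 10, 13, 26 (19, 25, 51) | 2 h | not listed | no | no |

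The protocol has 8 two-hour visits, the last at dose 26. The SAP has 4, the last at dose 4 in Week 7, plus 1 untimed visit; 3 are absent (4 + 1 + 3 = 8). Relative to the protocol's DSMB review, the SAP adds exactly one visit, and it is the one without a fixed time.

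**Step 2: how far timing alone could move a Visit 7 value.** The documents give neither a half-life nor the spread of Visit 7 sampling times. Assume mono-exponential decline after the infusion, a half-life h of 8 to 24 hours, and a draw t between 0 and 8 hours after the infusion ends. Then

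C(t) / C(2 h) = 2^((2 − t)/h)

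- h = 8, t = 0: 2^(2/8) = 1.19
- h = 8, t = 8: 2^(−6/8) = 0.59
- h = 24, t = 0: 2^(2/24) = 1.06
- h = 24, t = 8: 2^(−6/24) = 0.84

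Timing alone would shift the value by +19% to −41% at an 8-hour half-life, and by +6% to −16% at 24 hours. A half-life of 6 hours widens the range: 2^(2/6) = 1.26 at 0 hours and 2^(−6/6) = 0.50 at 8 hours.

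**Step 3: expected carry-over.** The dosing interval is 14 × 24 = 336 hours. At the longest assumed half-life, the fraction left is 2^(−336/24) = 2^(−14), about 0.006%; shorter half-lives leave less. This agrees with protocol 2.5, which reports that "there were only measurable levels of drug detected through 72 hours following a dose and were thereafter undetectable". With constant clearance, the 2-hour level should therefore be nearly flat across doses. The review could show a departure from that, such as a change in clearance, and for this the samples must be drawn at a common time.

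**The case against.** The case for leaving this alone has several parts.

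- **Repeated dosing is still observed.** A reader might infer that exposure over repeated dosing cannot be judged at all. The documents do not support that. Doses 1 to 4 keep comparable 2-hour samples, with later samples after doses 1 and 4. Visit 7 can be analyzed by actual time, and SAP 3.2.5 refers population PK to a separate plan (protocol 7.9.5 also plans it, although protocol 2.5 says no formal population PK analysis will be done).
- **The protocol's DSMB review is intact.** It covers Visits 1 to 4, all of which keep 2-hour samples, and the panel has a clinical pharmacologist. This stands. The problem is the visit that the SAP adds.
- **The size rests on assumptions.** The half-life and the 0-to-8-hour window are both assumed, and at 24 hours the shift is modest. This stands. Nor can one say that timing would dominate the Visit 7 comparison, because the documents give no between- or within-subject variability.
- **The absent visits may be deliberate.** A reader might infer that the SAP dropped Visits 10, 13 and 26 by mistake. The supplied protocol is the original of 20 February 2015, and the SAP appears to follow a later version: it admits cirrhosis only (Ishak 5 or 6), uses nondosing visits and adds histology endpoints. An amendment not supplied may have changed the PK schedule, perhaps to suit population modeling. The documents settle neither reading.
- **PK is descriptive here.** No efficacy endpoint, type I error rate or power figure is affected. This stands and limits the severity.

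None of this removes the conflict among SAP 10.1, 10.2 and 12, which holds whichever protocol version applied.

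**Conclusion.** The point holds as an inconsistency within the SAP. Visit 7 does not meet the 2-hour definition in SAP 10.2, yet SAP 12 has it reviewed as Cmax beside four visits that do. In that review sampling time is confounded with dose number, and on the 2-hour measure exposure is not followed beyond dose 4 of 26. This conclusion needs only the text.

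The size is illustrative: a factor of 1.19 to 1.06 for a draw at 0 hours and 0.59 to 0.84 for one at 8 hours, assuming mono-exponential decline and a half-life of 8 to 24 hours.

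The absence of Visits 10, 13 and 26 is a discrepancy to reconcile, not a demonstrated SAP error. The correction should be made because a safety-review measure is mislabeled; the trial's efficacy conclusions do not depend on it.

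**What to change.** In SAP 10.1, 11 and 12, limit the Cmax-by-visit summaries and the DSMB Cmax review to samples drawn at about 2 hours after the end of infusion, judged by recorded actual time. State the tolerance around 2 hours in advance; the SAP gives none. Use Visit 7 samples outside it only in analyses by actual time, such as the population PK model. State also whether such a sample counts as a Cmax sample for the PK set.

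The alternative is to give Visit 7 the 2-hour nominal time in protocol 6.5, provided the protocol version in force allows it and the samples have not already been drawn.

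Separately, reconcile the SAP's PK schedule with the protocol version in force and state whether Visits 10, 13 and 26 are sampled. If they are, add them to SAP 10.1 and the by-visit tables. If an amendment removed them, adding table rows would achieve nothing, and restoring the samples would take a protocol change and further blood draws.

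The first change costs SAP wording, table shells and some Visit 7 values in the DSMB table. It depends on clock times being captured. The SAP listing calls for date and time, but protocol 6.5 asks explicitly only for the collection date in the eCRF, so this should be confirmed.

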10.2. Plasma Pharmacokinetic Parameters

GR-MD-02 plasma concentrations will be used to evaluate systemic exposure following multiple dosing. Based on the high correlation between the area under the concentration-time curve and C_{max} of GR-MD-02 in the Phase 1 clinical study (Galectin 2014) ($p < 0.001$, $r^2 = 0.91$), the plasma levels at 2 hours (approximate C_{max}) following the dose of GR-MD-02 will be used to estimate the systemic exposure and to assess the attainment of the steady state of GR-MD-02.

All PK analyses will be conducted by the Department of Clinical Pharmacology, PPD, Inc., Richmond, VA, USA.

11. Interim Analysis

An interim analysis of PK data is planned for the first Data Safety Monitoring Board (DSMB) meeting. It is expected that PK analysis will be performed on the GR-MD-02 plasma concentrations for the first 30 subjects after Infusion Visits 1, 2, 3, 4 and 7. There should be approximately 10 subjects who received 2 mg/kg and 10 subjects who received 8 mg/kg in this group of subjects.

12. Data Safety Monitoring Board

An independent Data Safety Monitoring Board (DSMB) will be composed of medical experts and an unblinded biostatistician who will not participate in the study. The DSMB will be responsible for periodically monitoring the safety of the clinical study and

providing recommendations for the study by reviewing the safety data at several predetermined times during the study and at any other time when it is determined by the DSMB or Galectin Therapeutics Inc that such a review is warranted.

The DSMB review will occur as follows:

- after the first 30 subjects in the study have received 7 doses of IMP;
- after the approximately 50% of subjects to be enrolled has received 13 doses of IMP;
- after 50% of subjects have received 26 doses of IMP.

In addition to review of the safety data, the first DSMB meeting will also assess GR-MD-02 C_{\max} plasma levels after Infusion Visits 1, 2, 3, 4 and 7 for the first 30 subjects.

13. References

Galectin Pharmaceuticals, Inc. A Multi-Center, Partially Blinded, Maximum Tolerated Multiple Dose Escalation, Phase 1 Clinical Trial to Evaluate the Safety of GR-MD-02 in Subjects with Non-Alcoholic Steatohepatitis (NASH) with Advanced Hepatic Fibrosis. 17 Jun 2014. Protocol No. GT-020. Version 4. 96p.



Huber, PJ. Robust Regression: Asymptotics, Conjectures and Monte Carlo. *Annals of Statistics*. 1973;1, 799–821.

Galectin Therapeutics Inc

GT-026

**A Multicenter, Randomized, Placebo-Controlled, Double-Blind,
Parallel-Group, Phase 2 Clinical Trial to Evaluate the Safety and Efficacy
of GR-MD-02 for the Treatment of Liver Fibrosis and Resultant Portal
Hypertension in Patients with NASH Cirrhosis**

The NASH-CX Trial

26 Jan 2018

Statistical Analysis Plan Addendum

Version 2.0

Prepared by:

PPD

[name]
[name]

The additional data analysis as listed below will be performed as post-hoc analysis. The main objective is to repeat primary and secondary analysis on the following subgroups:

- a. Patients with baseline (BL) varices, and patients without BL varices.
- b. Patients with MPH (baseline HVPG 6 to <10 mmHg) and patients with CSPH (baseline HVPG \geq 10 mmHg)

For definition of analysis set and other terminology or abbreviation, please refer to final SAP. However, the subject who was randomized but have not received any treatment will be removed from all analysis sets used in post-hoc. In addition, the missing value at scheduled visit will be imputed by result from subsequent unscheduled visit. For example, if a subject's HVPG at Week 53-55 visit was not collected, but there's a subsequent unscheduled visit with valid result, this unscheduled result will be used as subject's HVPG result at Week 53-55.

For LOCF analysis, include all patients that had an early termination visit, and carry forward their last observation result.

Analyses on Primary Endpoint HVPG

1. Perform ANCOVA to determine effect of varices on HVPG on FAS LOCF dataset:
 - a. Week 53/55 HVPG is used as dependent with BL HVPG as covariate, and with dose, varices and dose varices interaction as fixed factors.
2. Run ANCOVA for FAS LOCF, mITT LOCF, and PP LOCF for HVPG with Least square difference (LSD) mean comparison (no Bonferroni correction) on subset of patients with / without baseline varices:
 - a. BL Change in HVPG vs dose with BL HVPG as a covariate (i.e. adjust for baseline HVPG)
 - b. Percent Change from BL HVPG vs dose with no covariate/no baseline adjustment
3. Perform similar ANCOVA/ANOVA analyses of MPH and CSPH for each subset, this would result in the following:
 - a. Analyses of patients without varices and with MPH – using FAS LOCF, mITT LOCF and PP LOCF for HVPG with LSD mean comparison (no Bonferroni correction) on:
 - i. ANCOVA for BL Change in HVPG vs dose with BL HVPG as a covariate (i.e. adjust for baseline HVPG)
 - ii. ANOVA for Percent Change from BL HVPG vs dose with no covariate/no baseline adjustment
 - b. Analyses of patients without varices and with CSPH - using ITT LOCF, mITT LOCF, and PP LOCF for HVPG with LSD mean comparison (no Bonferroni correction) on:
 - i. ANCOVA for BL Change in HVPG vs dose with BL HVPG as a covariate (i.e. adjust for baseline HVPG)
 - ii. ANOVA for Percent Change from BL HVPG vs dose with no covariate/no baseline adjustment

- c. Analyses of patients with varices and with MPH (6 to <10 mmHg) -- using ITT LOCF, mITT LOCF and PP LOCF for HVPG with LSD mean comparison (no Bonferroni correction) on:
 - i. ANCOVA for BL Change in HVPG vs dose with BL HVPG as a covariate (i.e. adjust for baseline HVPG)
 - ii. ANOVA for Percent Change from BL HVPG vs dose with no covariate/no baseline adjustment
- d. Analyses of patients with varices and CSPH (≥ 10 mmHg) -- using ITT LOCF, mITT LOCF, and PP LOCF for HVPG with LSD mean comparison (no Bonferroni correction) on:
 - i. ANCOVA for BL Change in HVPG vs dose with BL HVPG as a covariate (i.e. adjust for baseline HVPG)
 - ii. ANOVA for Percent Change from BL HVPG vs dose with no covariate/no baseline adjustment

Analyses on Secondary Endpoint Collagen Proportional Area (CPA)

All post-hoc analysis performed on HVPG parameter will be repeated for Collagen Proportional Area (CPA).

Analyses on Secondary Endpoints using FAS set

1. Perform BL Change vs. Dose using MMRM model for continuous data and Ordinal Logistic Regression (OLR) Analysis for categorical data for the following datasets: all data, With Varices, Without Varices, Without Varices and MPH, Without Varices and CSPH, With Varices and MPH, and With Varices and CSPH.
2. The change from baseline at Week 53/55 of categorical variable will be the response and treatment will be explanatory variable in OLR model. If Week 53/55 is missing, LOCF rule will be applied for imputation. The change from baseline will be classified to Decrease, No Change and Increase. The result of odds ratio and its 95%CI as well as p-value from Wald Chi Square test will be presented in the table. The lowest level ie Decrease is the event level in response.
3. The change from baseline at each visit of continuous variable will be the dependent variable in MMRM analysis. Baseline is the covariate and treatment, visit and interaction of treatment and visit are factors. If scheduled assessment is missing and a subsequent unscheduled assessment is available, the scheduled assessment will be imputed by unscheduled assessment.
4. The following parameters will be analyzed:
 - a. Change in NAFLD Activity Score (OLR) (LVBNAS)
 - b. Change in each Component of the NAFLD Activity Score:
 - i. Change in hepatocyte ballooning score (OLR)
 - ii. Change in inflammation (OLR)
 - iii. Change in steatosis/fat (OLR)
 - c. Change in Fibrosis Staging Score (OLR)

- i. Ishak staging score (OLR)
 - ii. Brunt staging score (OLR)
 - d. Change in FibroTest Score (MMRM)
 - e. Change in each Component of the FibroTest Score:
 - i. Change in Alpha2 Macroglobulin (MMRM)
 - ii. Change in Haptoglobin (MMRM)
 - iii. Change in Apolipoprotein A1 (MMRM)
 - iv. Change in Gamma-glutamyl transpeptidase, GGT (MMRM)
 - v. Change in Total Bilirubin (MMRM)
 - vi. Change in Alanine Transaminase, ALT (MMRM)
 - f. Change in ELF Score (MMRM)
 - g. Change in each Component of the ELF Score:
 - i. Change in tissue inhibitor of metalloproteinases 1, TIMP-1 (MMRM)
 - ii. Change in amino-terminal propeptide of type III procollagen, PIIINP (MMRM)
 - iii. Change in hyaluronic acid, HA (MMRM)
 - h. Change in AST/ALT Ratio (MMRM)
 - i. Change in Platelet Count (MMRM)
 - j. Change in ACTITEST Score (MMRM)
 - k. Change in GAL-3 (biomarker, MMRM)
5. Perform Chi Square Test without correction on overall data as well as the subset Without Varices for the following:
 - a. All Complications (for patients with at least one complication)
 - b. Each separate complication
 - c. Perform all analyses in a through e above also for combined active groups (GR2 + GR8) vs. placebo

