8.2. Key Secondary Efficacy Endpoints

There are six key secondary efficacy endpoints: CPA, Ishak histopathological stage, FibroScan[®], MBT, Brunt-Kleiner histopathological stage and complications of cirrhosis.

CPA

CPA will be used to measure liver collagen (a surrogate for fibrosis) by evaluation of liver biopsy at screening and 14 to 28 days after final dose (53 to 55 weeks). A single experienced pathologist, [name] (INNOVA Medical Center), will evaluate all liver biopsies at a central pathology laboratory.

The CPA will be summarized for the FAS population by visit and treatment group, for all scheduled visits, along with the change from baseline descriptively in a summary table and graphically.

Ishak histopathological stage

Fibrosis will be evaluated by liver biopsy and be staged according to the Ishak histopathological stage (0-6) at screening and 14 to 28 days after final dose (53 to 55 weeks). The number and percentage of subjects by Ishak histopathological stage will be summarized using the FAS population by treatment group. The number and percentage of subjects changing in Ishak histopathological stages will also be presented.

FibroScan[®]

FibroScan[®] will be only performed at the study centers where it is available and used to evaluate liver stiffness which is recorded as the pressure measurement of kPa at the scheduled visits.

The FibroScan[®] (if available) will be summarized for the FAS population by visit and treatment group, for all scheduled visits, along with the change from baseline descriptively in a summary table and graphically.

MBT

The MBT will only be performed at the study centers where it is approved. The cumulative percentage dose recovery of the metabolized ¹³C-methacetin 30 minutes after ingestion of the test substrate will be used as the MBT parameter for this study. Delta over baseline (DOB) with corresponding time point (T_n) will be collected on the eCRF.

The $cPDR_{30}$ is defined as:

$$cPDR_{30} = \frac{\frac{T_1}{60} \cdot PDR_1}{2} + \sum_{i=2}^n \frac{\frac{T_i - T_{i-1}}{60} \cdot (PDR_i + PDR_{i-1})}{2}$$

where $PDR_i = 1.817853 \times DOB_i \times w^{0.5378} \times h^{0.3963}$, $w = weight$ (kg), $h = height$ (cm).

Brunt-Kleiner histopathological stage

Fibrosis will be evaluated by liver biopsy and be staged according to the Brunt-Kleiner histopathological stage (0-4) at screening and 14 to 28 days after final dose (53 to 55 weeks).

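### The post-hoc ordinal models for the NAFLD Activity Score and its components keep only the direction of change and omit baseline score, which costs power and exposes the odds ratio to chance imbalance

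*SAP*

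**What the plan says.** The relevant text is in the SAP Addendum of 26 January 2018, under Analyses on Secondary Endpoints using FAS set.

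- **Categorical endpoints (item 2).** "The change from baseline at Week 53/55 of categorical variable will be the response and treatment will be explanatory variable in OLR model". Then: "The change from baseline will be classified to Decrease, No Change and Increase". Decrease is the event level, and "The result of odds ratio and its 95%CI as well as p-value from Wald Chi Square test will be presented in the table".
- **Continuous endpoints (item 3, MMRM).** "Baseline is the covariate and treatment, visit and interaction of treatment and visit are factors".
- **Scores under the ordinal model (item 4).** There are six: the NAFLD Activity Score (NAS); its ballooning, inflammation and steatosis components; and the Ishak and Brunt stages.
- **Datasets (item 1).** All data, with varices, without varices, and four cells: "Without Varices and MPH, Without Varices and CSPH, With Varices and MPH, and With Varices and CSPH". Six scores in seven datasets make 6 × 7 = 42 ordinal analyses.

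Elsewhere in the addendum, the HVPG section uses the Week 53/55 value as dependent variable with baseline HVPG as covariate (item 1), and adjusts change in HVPG for baseline (items 2 and 3). It explicitly leaves baseline out only for percent change in HVPG. The addendum describes all of its analyses as post hoc and claims no power for them.

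**The concern.** These scores are bounded. A subject at the lowest grade cannot decrease and one at the highest cannot increase, so baseline score partly determines the response class, yet the model ignores it. Such subjects can enter the trial. Protocol inclusion criterion 2b admits a biopsy with any amount of fat and does not require ballooning or inflammation. Entry is limited to the top of the Ishak scale (stages 5 and 6 in SAP section 3.1, 4 to 6 in the protocol), so a stage 6 subject can never be an Increase. SAP section 4.2 gives no stratification factor that would balance these scores between arms.

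Two things are lost. Ignoring baseline and counting a one-point and a three-point fall alike both cost power. And if one arm happens to start with higher scores, its odds of Decrease rise without any drug effect. The second matters most in the varices-by-HVPG cells, where the tabulated odds ratios, intervals and p-values could be over-read.

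**Working it through.** **The plan's own figure.** The documents state no power for any histology model. The only design figure is for HVPG: difference 2 mm Hg, SD 3 mm Hg, two-sided 0.05, 80% power, 25% dropout (protocol section 7.6). A two-sample t-test needs 37 evaluable per arm, and 37 / 0.75 = 49.3, so 50 against the planned 52. The plan is slightly conservative: 52 × 0.75 = 39 evaluable gives 82.8% power. I use 39 per arm below.

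**Models compared**, active against placebo, two-sided Wald test at 0.05, with T = treatment and B = baseline score:
- (a) addendum: logit P(sign of change ≤ k) = α_k + βT
- (b) as (a), plus γB
- (c) full change score, T only
- (d) logit P(Week 53/55 score ≤ k) = α_k + βT + γB

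**Assumed inputs.** For NAS, baseline is normal with mean 4.5 and SD 1.5. The final value is 4.5 + ρ(baseline − 4.5) + 1.5√(1 − ρ²)Z, minus a benefit of 1.1, 0.9 or 0.75 points at ρ = 0.3, 0.5 or 0.7. Both are rounded and limited to 0–8. Benefits were chosen so that (d) has about 82% to 89% power. The component ranges, and the Ishak and Brunt baseline mixes and transition rates, are also assumptions.

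**Power, 39 per arm, 3000 simulated trials** (Monte Carlo SE at most √(0.25/3000) = 0.9 points):

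| Score | (a) | (b) | (c) | (d) | (d) − (a) |
|---|---|---|---|---|---|
| NAS, ρ 0.3 | 63.2% | 75.9% | 73.5% | 89.4% | 26.2 |
| NAS, ρ 0.5 | 61.4% | 70.4% | 70.0% | 82.5% | 21.1 |
| NAS, ρ 0.7 | 67.5% | 72.5% | 74.4% | 81.9% | 14.4 |
| Steatosis type, 0–3 | 59.8% | 73.1% | 61.9% | 77.9% | 18.1 |
| Ballooning type, 0–2 | 69.9% | 83.5% | 72.3% | 85.9% | 16.0 |
| Ishak, 30% at 5, 70% at 6 | 77.7% | 79.9% | 79.7% | 80.2% | 2.5 |
| Brunt, 95% at 4 | 79.4% | 42.7% | 80.5% | 77.3% | −2.1 |

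In the Brunt row, (b) failed to fit in 47% of trials.

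For NAS, adding baseline alone recovers 5 to 13 points and keeping the size of change alone recovers 7 to 10. For the components, baseline recovers 13 to 14 points and the size of change only about 2.

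Other simulations agree. A generic four-level score with 40 per arm, a 0.6 SD shift and 300 trials gave 43% against 68% (correlation 0.4) and 59% against 82% (correlation 0.6). A further run for NAS and its components at 39 per arm, with its own assumed inputs, gave 46–70% for (a) and 73–88% for (d). Over all runs the loss is roughly 14 to 28 points.

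**Chance imbalance with no treatment effect.** Let the active arm start one standard error higher. For NAS that is 1.5√(2/n): 0.29 points at n = 52 per arm, 0.47 at 20, 0.67 at 10. For Ishak it is √(2 × 0.7 × 0.3 / n) in the proportion at stage 6: 0.09, 0.145, 0.205. Subset sizes of 20 and 10 are assumed. Odds ratio for Decrease:

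| Per arm | NAS, (a) | Ishak, (a) |
|---|---|---|
| 52 | 1.15–1.20 | 1.16 |
| 20 | 1.22–1.37 | 1.22 |
| 10 | 1.33–1.49 | 1.38 |

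Under (d) it is 0.98 to 1.02 throughout.

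**Type I error.** Averaged over randomisations, (a) rejects in 4.8% to 6.1% of null trials at 39 to 52 per arm.

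**The case against.** The strongest case against is about weight.

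- **Post-hoc status.** These models sit outside the gatekeeping sequence of SAP section 8.2.1 and claim no power, and NAS and its components appear in no endpoint list of the main SAP. A shortfall here changes no confirmatory conclusion. That stands and lowers the stakes. It does not remove the gain, since effect estimates and p-values will still be reported.
- **Consistency with the rest of the plan.** The main SAP tests Ishak and Brunt-Kleiner more coarsely still, by Fisher's exact test on at least one stage of change, and the addendum elsewhere omits baseline on purpose. This is true, but for percent change in HVPG the omission is stated, whereas item 2 gives no reason.
- **Adjustment has a price.** This also stands. With Ishak at 10 per arm under the null, fits failed in 7% of trials for (a), 42% for (b) and 12% for (d). For NAS at 20 per arm, (d) rejected in 7.4% of null trials against 5.6% for (a), so its Wald test is slightly liberal in small subsets. For NAS at 10 per arm, however, (d) failed in at most 0.3% of trials.

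A reader might infer that all six scores lose much power. The results do not support that. Fibrosis stage starts at or next to the ceiling and most changes are plausibly one stage, so direction keeps nearly all the information.

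**Conclusion.** The point holds for the NAS and its components. Item 2 discards the baseline score and the size of change, at a cost of roughly 14 to 28 points of power with about 39 to 40 subjects per arm. A one-standard-error imbalance can by itself move the NAS odds ratio to about 1.15–1.20 in the full sample and about 1.3–1.5 in a cell of 10 per arm. The size of both effects rests on assumed score ranges, baseline distributions, correlations, benefits and subset sizes. The direction follows from the model as written.

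For Ishak the power loss is about 2 to 3 points and for Brunt there is none, so what remains there is a reporting matter. It is also tempting to call the planned tests biased or their p-values invalid. Randomisation makes the imbalance zero on average and type I error stays near 5%. The weakness is lost precision and the reading of a particular sample, not validity.

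**What to change.** 1. For the NAS and its ballooning, inflammation and steatosis components, fit a proportional-odds model to the Week 53/55 score with treatment and baseline score as explanatory variables. At minimum, add baseline score to the planned model.
2. Report the planned three-class, treatment-only result beside it, with each model labelled so that the change is visible.
3. For Ishak and Brunt, give shift tables from baseline stage by arm, and note that subjects at the top stage cannot worsen.
4. Tabulate baseline score distributions by arm in every subset analysed.
5. State in advance that where a subset is very small or its baseline nearly constant, so that the adjusted model does not converge, the unadjusted model or a descriptive table is kept.

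The cost is one extra covariate, one changed response variable and a few tables, with no new data. The downsides are failure to converge, and a slightly liberal Wald test, in the smallest cells.
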